#### **Dosing Criteria for Cycles** $\geq 2$

Following completion of the first treatment cycle, participants may receive additional treatment with sabestomig when the following conditions are met:

- The participant does not meet any criteria for discontinuation of IMP as listed in Section 7.1
- The participant has adequate marrow, renal, and liver function, outlined in Table 9. Note: Laboratory evaluations must be performed up to 3 days prior to initiation of each cycle of treatment; transfusion and granulocyte colony stimulating factor support is permissible.
- If the participant experiences an AE following administration of study intervention in the previous dosing cycle, the participant must not meet criteria for dose omission or permanent discontinuation and must meet retreatment guidelines as outlined in the toxicity management guidelines as defined in Appendix I.

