## 6.6.3 Definition of Dose-limiting Toxicity

The DLTs will be evaluated during Part A Dose Escalation. The DLT evaluation period will be 28 days from the first dose of sabestomig on Cycle 1 Day 1. Participants who do not remain in the study for the entire duration of the DLT evaluation period, for reasons other than DLT, will be considered non-evaluable for DLT evaluation and will be replaced with another participant at the same dose level if needed to ensure a minimum of CCI evaluable participants in the ATD and mTPI-2 cohorts, respectively.

A DLT will be defined during Part A Dose Escalation as any  $\geq$  Grade 3 AE as per NCI CTCAE version 5 unless unequivocally due to underlying malignancy or an extraneous cause. The modifications and exceptions to this are detailed below.

The following conditions will be considered as DLTs:

- Any death not clearly due to the underlying disease or extraneous causes.
- Grade 4 imAE.
- Any  $\geq$  Grade 3 non-infectious pneumonitis irrespective of duration.
- Any  $\geq$  Grade 3 non-infectious colitis irrespective of duration.
- Liver transaminase elevation:
  - Isolated liver transaminase elevation > 5 x but  $\le 10$  x ULN that does not downgrade to AST/ALT  $\le 3$  x ULN or less within 7 days after onset with optimal medical management including systemic corticosteroids.
  - Transaminase elevation > 10 x ULN regardless of duration or reversibility.
  - Isolated TBL elevation > 3 x ULN that does not downgrade to ≤ 1.5 x ULN within 7 days after onset with optimal medical management (for participants with Gilbert's syndrome: TBL > 3 x ULN and doubling of direct bilirubin that does not downgrade to baseline value within 7 days).
  - Any increase in AST/ALT > 3 x ULN and concurrent increase in TBL  $\ge$  2 x ULN, regardless or duration or reversibility, where no other reason, other than the investigational product(s), can be found to explain the combination of increases (for participants with Gilbert's syndrome: TBL > 3 x ULN and doubling of direct bilirubin that does not downgrade to baseline value within 7 days).
- Any Grade 3 imAE, including rash, pruritus, or diarrhea (NOTE: this excludes colitis or pneumonitis, as these AEs are already defined above), that does not downgrade to Grade 2 or less within 7 days after onset of the event despite maximal supportive care including systemic corticosteroids.

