- Renal disorders: Nephritis, nephropathy, elevated serum creatinine, and glomerulonephritis/sclerosis
- Cardiac disorders: Myocarditis and pericarditis
- Skin disorders: Rash, pruritus, dermatitis, vitiligo, psoriasis, SJS/TEN, pemphigus, and lichen planus
- Other rare imAEs including encephalitis, hemophagocytic lymphohistiocytosis, myositis/polymyositis, uveitis, iridiocyclitis, arthritis, Guillain-Barre syndrome, myasthenia gravis, vasculitis, hemolytic anemia, aplastic anemia, anemia, and sarcoidosis

Other aEs which are considered to be AESIs with sabestomig include but are not limited to:

- Infusion-related reactions; hypersensitivity including anaphylactic/anaphylactoid and other allergic reactions
- Immune complex disease and vasculitis
- Cytokine release syndrome

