			
 
Consider, as necessary, discussing with study physician if no resolution to Grade ≤1 in 3 to 4 days.
 

	Grade 3 or 4	Grade 3	For Grade 3 or 4
		
 
Hold investigational
 
drug(s) until resolution to
 
	
 
Promptly initiate empiric IV methylprednisolone 1 to 2 mg/kg/day or equivalent.
 

		Grade $\leq 1$ ; investigational	
 
Monitor stool frequency and volume and maintain hydration.
 

		drug(s) can be resumed after completion of steroid	
 
Urgent GI consult and imaging and/or colonoscopy as appropriate.
 

		taper. Permanently discontinue investigational drug(s) for Grade 3 if toxicity does not improve to Grade $\leq 1$ within 14 days.	
 
If still no improvement within 2 days, continue steroids and promptly add further immunosuppressants (eg, infliximab at 5 mg/kg IV, may be repeated at 2 and 6 weeks after initial dose at the discretion of the treating provider). Caution: Ensure GI consult to rule out bowel perforation and refer to infliximab label for general guidance before using infliximab.
 

		• Permanently discontinue investigational drug(s) for any grade of intestinal perforation in any patient treated with study	
 
If perforation is suspected, consult a surgeon experienced in abdominal surgery immediately without any delay.
 

Adverse Events	Severity Grade of the Event	Dose Modifications	Toxicity Management
		• Permanently discontinue investigational drug(s) for recurrent ≥ Grade 3 colitis	
		Grade 4 Permanently discontinue investigational drug(s).	
Nephritis or renal	Any Grade	General Guidance	For Any Grade
dysfunction	(Refer to NCI CTCAE applicable		
 
Consult a nephrologist.
 

(elevated serum creatinine)	version in study protocol for defining the CTC grade/severity)		
 
Monitor for signs and symptoms that may be related to changes in renal function (eg, routine urinalysis, elevated serum BUN and creatinine, decreased creatinine clearance, electrolyte imbalance, decrease urine output, or proteinuria).
 

			
 
Patients should be thoroughly evaluated to rule out any alternative etiology (eg, disease progression, infections, recent IV contrast, medications, fluid status).
 

			
 
Consider using steroids in the absence of a clear alternative etiology even for low-grade events (Grade 2), in order to prevent potential progression thigher grade events.
 

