	Grade 2	
 
For acute motor neuropathies or neurotoxicity, hold investigational drug(s) until resolution to Grade ≤ 1.
 
For sensory neuropathy/neuropathic pain, consider holding investigational drug(s) until resolution to Grade ≤ 1.
 
Permanently discontinue investigational drug(s) if Grade 2 imAE does not resolve to Grade ≤ 1 within 30 days.
 
If toxicity worsens, then treat as Grade 3 or 4.
 
	
 
For Grade 2
 
Consider, as necessary, discussing with the study physician.
 
Obtain neurology consult.
 
Sensory neuropathy/neuropathic pain may be managed by appropriate medications (eg, gabapentin or duloxetine).
 
Promptly start systemic steroids prednisone 1 to 2 mg/kg/day PO or IV equivalent.
 
If no improvement within 2 to 3 days despite 1 to 2 mg/kg/day prednisone PO or IV equivalent, consider additional workup and promptly treat with an additional immunosuppressant (eg, IV IG or other immunosuppressant depending on the specific imAE)
 

	Grade 3 or 4	For Grade 3 or 4 Permanently discontinue investigational drug(s).	
 
For Grade 3 or 4
 
Consider, as necessary, discussing with study physician.
 
Obtain neurology consult.
 
Consider hospitalization.
 
Promptly initiate empiric IV methylprednisolone 1 to 2 mg/kg/day or equivalent.
 
If no improvement within 2 to 3 days despite IV corticosteroids, consider additional workup and promptly treat with an additional immunosuppressant depending on the specific imAE).
 

Adverse Events	Severity Grade of the Event	Dose Modifications	Toxicity Management
			– Once stable, gradually taper steroids over $\ge 28$ days.
Peripheral neuromotor	Any Grade	General Guidance	For Any Grade
syndromes	(Refer to NCI CTCAE applicable version in study protocol for defining the CTC grade/severity)		
 
The prompt diagnosis of immune-mediated peripheral neuromotor syndromes is important, since certain patients may unpredictably experience acute decompensations that can result in substantial morbidity or in the worst case, death. Special care should be taken for certain sentinel symptoms that may predict a more severe outcome, such as prominent dysphagia, rapidly progressive weakness, and signs of respiratory insufficiency or autonomic instability.
 

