		participant is assessed by a cardiologist on a regular basis.	infliximab at 5 mg/kg IV which may be repeated at 2 and 6 weeks after initial dose at the discretion of the treating provider). Caution: It is important to rule out sepsis and refer to infliximab label for general guidance before using infliximab. Infliximab is contraindicated for patients who have heart failure.
			
 
Close monitoring for worsening symptoms or signs of myocarditis needs to be performed before and during the tapering of corticosteroid or other immunosuppressive.
 

			- If patient continues to worsen, treat as Grade 3/4.
	Grade 3 or 4	• Permanently discontinue	
 
Monitor symptoms daily, hospitalize.
 

		investigational drug.	
 
Supportive intensive care (eg, oxygen, circulatory support including hemodynamic, temporary pacing, arrhythmia treatment as needed).
 

			
 
Consider laboratory workup and imaging as described under general guidance for all grades of myocarditis.
 

			
 
Consider urgent cardiology consultation to determine if and when to complete diagnostic procedures, including a cardiac biopsy.
 

			
 
Promptly start high-dose pulse high-dose IV methylprednisolone 1 gram/day for 3 days and then 2 mg/kg prednisone daily. Consider initiation ACE inhibitors or ARBs for LV dysfunction, if clinically appropriate.
 

			
 
If no improvement within 3 to 5 days despite IV methylprednisolone, consider starting additional immunosuppressives such as tacrolimus or mycophenolate mofetil. In unstable patients who do not respond to corticosteroids, consider antithymocyte globulin or IV immunoglobulin.
 

			
 
Close monitoring for worsening symptoms or signs of myocarditis needs to be performed before and during the tapering of corticosteroid or other immunosuppressive.
 

Adverse Events	Severity Grade of the Event	Dose Modifications	Toxicity Management
Myositis/ Polymyositis	Any Grade	General Guidance	For Any Grade

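### A Grade 3 immune-mediated event that ends treatment for good can be counted as no DLT under Protocol 6.6.3 if it downgrades within 7 days

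*Protocol*

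**What the plan says.** **DLT definition (Protocol 6.6.3).** The starting rule covers every AE of Grade 3 or above, apart from those clearly due to the lymphoma or another outside cause, and announces modifications and exceptions. Pneumonitis gets no grace period ("Grade 3 non-infectious pneumonitis irrespective of duration"), and neither does colitis. Two liver rules also ignore duration: transaminases above 10 x ULN, and AST/ALT above 3 x ULN together with bilirubin of at least 2 x ULN. All other Grade 3 imAEs fall under one bullet, whose examples are rash, pruritus and diarrhea. It names them as DLTs with this condition: "this excludes colitis or pneumonitis, as these AEs are already defined above), that does not downgrade to Grade 2 or less within 7 days". Grade 3 CRS has a similar condition of 72 hours. Permanent discontinuation is not a DLT criterion.

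**What counts as an imAE (Protocol 8.3.6).** The list, which is open-ended, includes "Cardiac disorders: Myocarditis and pericarditis" and "Renal disorders: Nephritis, nephropathy, elevated serum creatinine, and glomerulonephritis/sclerosis". Neurotoxicity and acute pancreatitis appear in the table of specific immune-mediated reactions in Appendix I.

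**What ends treatment (Appendix I, Protocol 6.1.2).** Appendix I sets the dose action by toxicity and grade. Section 6.1.2 ties redosing from Cycle 2 onward to it: "the participant must not meet criteria for dose omission or permanent discontinuation".

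**How the count is used.** DLT incidence is a Part A primary endpoint (Table 5). It drives the Table 15 decisions, the rule that closes a dose as unsafe, the step-size caps in 6.6.1 and the isotonic MTD estimate in 9.4.3.1.

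**The concern.** A toxicity severe enough to bar a participant from any further dose is normally what a DLT count is meant to catch. Here such an event can be missed because it responds to treatment. Grade 3 myocarditis shows the problem: Appendix I stops the drug and directs "Promptly start high-dose pulse high-dose IV methylprednisolone 1 gram/day for 3 days and then 2 mg/kg prednisone daily". If that brings the event to Grade 2 within 7 days, the imAE bullet no longer names it as a DLT. The participant is then not dropped from the denominator but counted as having tolerated the dose. The ordering is also odd, because Grade 3 colitis is always a DLT although Appendix I says that "drug(s) can be resumed after completion of steroid" taper, once the event has resolved.

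At stake are individual escalation decisions in small cohorts, and the MTD estimate built from the same counts.

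**Working it through.** **Step 1. The two rules side by side, at Grade 3.**

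| Event | 6.6.3 | Appendix I |
|---|---|---|
| Pneumonitis | DLT at once | Permanent stop |
| Transaminases > 10 x ULN | DLT at once | Stop |
| Colitis | DLT at once | Hold; may resume |
| Myocarditis | 7-day condition | Permanent stop |
| Nephritis / renal dysfunction | 7-day condition | Permanent stop |
| Neurotoxicity | 7-day condition | "For Grade 3 or 4 Permanently discontinue investigational drug(s") |
| Acute pancreatitis | 7-day condition | "For Grade 3 or 4 Permanently discontinue investigational drug(s") |
| CRS | 72-hour condition | Permanent stop |

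The last five rows are the gap.

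**Step 2. One participant followed through.** Suppose Grade 3 myocarditis starts on Day 10, the drug is stopped for good, and Grade 2 is reached on Day 16, 6 days after onset. Under the imAE bullet this is not a DLT. Section 7.1 keeps the participant in the study after stopping the drug. Section 6.6.6 asks only for some sabestomig and completion of the 28 days, so the participant is evaluable. In the posterior Beta(1+a, 1+b) of 6.6.1.2 the participant adds 1 to b, the count without a DLT.

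**Step 3. Reproduce Table 15.** Inputs from 6.6.1.2: prior Beta(1,1), target 30%, equivalence interval (25%, 33%), dose closed (DU) if P(rate > 30%) is at least 80%. The decision is the sub-interval (width 0.33 − 0.25 = 0.08) with the largest unit probability mass. Of the 54 cells for 0 to 4 DLTs and 1 to 12 participants, 48 match directly. The other 6 (0/1, 0/2, 1/1, 1/2, 1/3, 3/12) are the overrides in footnotes a, b, c and e.

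For x DLTs in n, P(rate > 0.30) = Σ (i = 0 to x) C(n+1, i) · 0.3^i · 0.7^(n+1−i):

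- 0/3: 0.7^4 = 0.240
- 1/3: 0.240 + 4 · 0.3 · 0.7^3 = 0.652
- 2/3: 0.652 + 6 · 0.3^2 · 0.7^2 = 0.916
- 1/6: 0.7^7 + 7 · 0.3 · 0.7^6 = 0.082 + 0.247 = 0.329
- 2/6: 0.329 + 21 · 0.3^2 · 0.7^5 = 0.647

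**Step 4. Effect of one such event on the decision.**

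| Not counted | Counted |
|---|---|
| 0/3, escalate | 1/3, stay |
| 1/3, stay | 2/3, dose closed |
| 1/6, escalate | 2/6, de-escalate |
| 2/9, escalate | 3/9, de-escalate |
| 3/12, escalate | 4/12, de-escalate |
| 0/6, escalate | 1/6, escalate (no change) |
| 1/9, escalate | 2/9, escalate (no change) |

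**Step 5. Effect on step size (6.6.1).** An uncounted imAE still above Grade 1 at 72 hours caps the next step at +100%. Counted as an imAE DLT, it caps the step at +50%.

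- From 225 mg, the planned step is 750 mg (+233%). The caps give 225 × 2 = 450 mg or 225 × 1.5 = 337.5 mg.
- From 750 mg, the planned step is 1500 mg (+100%). It is allowed under the first cap; the second gives 750 × 1.5 = 1125 mg.
- From 1500 to 2000 mg (+33%), neither cap binds.

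**The case against.** **The opening rule may already catch these events.** Any Grade 3 AE is a DLT by default, and 6.6.3 has a separate list of what is not a DLT. That list contains time-limited exemptions (fatigue, endocrine disorders, local inflammatory reactions, laboratory abnormalities), but not a recovering Grade 3 imAE. Nor does redundancy settle the matter, since the list of DLTs repeats other events that are DLTs by default. This stands to the extent that a reader who infers a certain miscount goes beyond the text. But on the strict reading the 7-day and 72-hour conditions would do nothing. The closing sentence of 6.6.3 does not resolve it: it is discretionary and is directed at AEs not listed or outside the window.

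**Stopping rules and DLT rules serve different purposes.** One protects the individual, the other finds a dose, and they need not coincide. That is fair in principle. However, 6.6.3 does drop the grace for pneumonitis and the two liver patterns that end treatment, so the omissions look unintended.

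**Other safeguards exist.** Accelerated titration ends at any Grade 2 TEAE, the step caps apply, and the Safety Review Committee sees all data. AEs leading to discontinuation are also a primary endpoint, and the RP2D does not rest on the MTD alone. All true; none corrects the DLT count.

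**Stronger readings the documents do not support.**

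- A reader might infer that only colitis and pneumonitis escape the grace. The liver bullets show otherwise.
- A reader might infer from the Note in 4.5 that myocarditis in Part A has no stopping rule at all. The 10% limit for Grade 3 or higher myocarditis in 4.5 covers Part A participants at the RP2D, as 9.5 confirms, and the sponsor's general safety criterion remains.
- A reader might count every Grade 3 creatinine rise. The existing exemption covers asymptomatic laboratory changes reversed within 7 days.
- A reader might attach a probability. No rate is given for these events. Section 2.3.1 reports all Grade 3 to 4 AEs with other anti-TIM-3 agents in about 4% to 11% of participants. Section 4.3.3 gives treatment-related Grade 3 rates of 9.2%, 8.2% and 0% for one combination, mostly rash. The events at issue are a subset of such AEs, with onset within 28 days and recovery within 7.

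**Conclusion.** The point holds as a gap or, at best, an ambiguity in the definition that feeds Table 15. On the most natural reading, Grade 3 myocarditis, neurotoxicity, clinical nephritis or acute pancreatitis that downgrades within 7 days can be recorded as no DLT although Appendix I ends treatment. The same applies to Grade 3 CRS that improves within 72 hours.

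The size is one decision per affected cell, as tabulated above; not every cell moves. This rests on the imAE bullet being a modification of the opening rule, and on the event downgrading in time. How often that would happen cannot be derived from the documents, and they do not say whether it has happened. The change is worth making because the affected cells include the first decision at a new dose and the remedy is small.

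**What to change.** 1. In Protocol 6.6.3, extend the NOTE in the imAE bullet. Grade 3 myocarditis, neurotoxicity, clinical nephritis, acute pancreatitis and any other Grade 3 imAE for which Appendix I requires permanent discontinuation become DLTs irrespective of duration.
2. State in the same place that the exemption for asymptomatic Grade 3 laboratory abnormalities reversed within 7 days, including isolated creatinine rises, still prevails.
3. Make Grade 3 CRS consistent between 6.6.3 and Appendix I.
4. If escalation is complete, add to SAP 4.5.10 a recount of Part A DLTs by dose level under this rule, beside the protocol count, with the isotonic estimate rerun.

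The cost is one extended NOTE, a CRS alignment, slightly more conservative escalation and one extra table. The data are already collected: Protocol 8.3.2 records dated grade changes and the action taken with the drug for each AE.

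As a purely editorial matter, SAP 4.5.10.1 should point to Protocol 6.6.3 for the DLT definition; 9.4.3.1, which it cites, contains none.

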- Grade 3 nausea, vomiting, or diarrhea that does not resolve to Grade 2 or less within 3 days of initiation of maximal supportive care.
- Neutropenia.
  - $\geq$  Grade 3 neutropenia, without associated fever or systemic infection, which does not improve by at least one grade within 7 days of onset.
- Thrombocytopenia:
  - Grade 4 thrombocytopenia lasting more than 7 days.
  - $\geq$  Grade 3 thrombocytopenia associated with a Grade  $\geq$  2 bleeding, which in the opinion of the Investigator, is related to study intervention.
- Grade 4 anemia not related to the underlying disease or any extraneous cause.

- Cytokine Release Syndrome (CRS):
  - Grade 4 CRS of any duration.
  - Grade 3 CRS that does not improve to Grade  $\leq 2$  within 72 hours.

The following conditions will not be considered as DLTs:

- Grade 3 fatigue lasting  $\leq$  7 days.
- Grade 3 endocrine disorder (thyroid, pituitary, and/or adrenal insufficiency) that is managed with or without systemic corticosteroid therapy and/or hormone replacement therapy with resolution of the symptoms within 14 days after treatment onset.
- Grade 3 inflammatory reaction attributed to a local antitumor response (eg, inflammatory reaction at sites of metastatic disease, lymph nodes) that resolves to ≤ Grade 1 within 7 days after onset.
- Vitiligo or alopecia of any AE Grade.
- Grade 3 or Grade 4 lymphopenia (unless associated with clinical sequelae).
- Grade 3 laboratory abnormalities that are not associated with clinical signs or symptoms (eg, hyperlipasemia or hyperamylasemia not associated with clinical signs or symptoms or radiographic features suggestive of pancreatitis) and are reversed with appropriate maximal medical intervention within 7 days.

Immune-mediated AEs are defined as AEs of an immune nature (ie, inflammatory) in the absence of a clear alternative etiology. In the absence of clinical abnormality, repeat laboratory testing will be conducted to confirm significant laboratory findings prior to designation as a DLT.

An AE not listed above or an AE meeting the DLT criteria above but occurring outside of the DLT-evaluation period, may be defined as a DLT after consultation with AstraZeneca and Investigators based on the emerging safety profile.

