#### **Dosing Modification and Toxicity Management Guidelines (TMGs) for Sabestomig**

#### General Considerations Regarding Immune-Mediated Reactions

#### These guidelines are provided as a recommendation to support Investigators in the management of potential imAEs.

Immune-mediated events can occur in nearly any organ or tissue, therefore, these guidelines may not include all the possible immune-mediated reactions. Investigators are advised to take into consideration the appropriate practice guidelines and other society guidelines (eg, NCCN, ESMO) in the management of these events. Refer to the section of the table titled "Other -Immune-Mediated Reactions" for general guidance on imAEs not noted in the "Specific Immune-Mediated Reactions" section. Early identification and management of imAEs are essential to ensure safe use of the study intervention. Monitor patients closely for symptoms and signs that may be clinical manifestations of underlying imAEs. Patients with suspected imAEs should be thoroughly evaluated to rule out any alternative etiologies (eg, disease progression, concomitant medications, infections). In the absence of a clear alternative etiology, all such events should be managed as if they were immune-mediated. Institute medical management promptly, including specialty consultation as appropriate. In general, withhold investigational drug(s) for severe (Grade 3) imAEs. Permanently discontinue investigational drug(s) for life-threatening (Grade 4) imAEs, recurrent severe (Grade 3) imAEs that require systemic immunosuppressive treatment, or an inability to reduce corticosteroid dose to 10 mg or less of prednisone or equivalent per day within 12 weeks of initiating corticosteroids.

Based on the severity of the imAE, treatment with sabestomig should be withheld and corticosteroids administered. Upon improvement to Grade  $\leq 1$ , corticosteroid should be tapered over  $\geq 28$  days. More potent immunosuppressive agents such as TNF inhibitors (eg, infliximab) should be considered for events not responding to systemic steroids. Alternative immunosuppressive agents not listed in this guideline may be considered at the discretion of the Investigator based on clinical practice and relevant guidelines. With long-term steroid and other immunosuppressive use, consider need for *Pneumocystis jirovecii* pneumonia (PJP, formerly known as *Pneumocystis carinii* pneumonia) prophylaxis, gastrointestinal protection, and glucose monitoring.

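### Protocol 6.6.3 gives immune-mediated Grade 3 diarrhea two DLT time rules with different clocks and no precedence, so one event can be classified two ways and the dose decision can change

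*Protocol*

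**What the plan says.** Protocol Section 6.6.3 starts from a default: any AE of Grade 3 or higher in the 28-day evaluation period is a DLT unless it is unequivocally due to the malignancy or an extraneous cause. It then adds: "The modifications and exceptions to this are detailed below". Two entries follow in the list of conditions that count as DLTs.

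- Immune-mediated events: "Any Grade 3 imAE, including rash, pruritus, or diarrhea", "that does not downgrade to Grade 2 or less within 7 days after onset of the event despite maximal supportive care including systemic corticosteroids". A note removes colitis and pneumonitis from this entry, because they have their own entries. Diarrhea is not removed.
- Gastrointestinal events: "Grade 3 nausea, vomiting, or diarrhea that does not resolve to Grade 2 or less within 3 days of initiation of maximal supportive care". The entry has no limit by cause.

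The same section supplies the definition that decides which events fall under the first entry: "Immune-mediated AEs are defined as AEs of an immune nature (ie, inflammatory) in the absence of a clear alternative etiology". Section 8.3.6 lists diarrhea among the gastrointestinal immune-mediated events that may be seen with sabestomig. The separate list of conditions that are not DLTs does not mention diarrhea.

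The SAP adds no rule. SAP Section 4.5.10.1 refers to protocol Section 9.4.3.1 for the definition of a DLT, but that section covers estimation of the maximum tolerated dose (MTD) and contains no such definition.

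**The concern.** An immune-mediated Grade 3 diarrhea falls within the scope of both entries. They differ in window (7 days against 3) and in clock (onset against start of maximal supportive care), and no text gives one precedence. Because the default already makes Grade 3 events DLTs, an entry with a time limit reads naturally as an allowance for events that resolve inside it. Here two allowances disagree about the same event.

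The classification feeds three things in Part A: the DLT count that enters Table 15, the 50% limit on the next dose increment when a cohort has one immune-mediated DLT (Section 6.6.1), and the DLT rates from which the MTD is estimated (Section 9.4.3.1).

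**Working it through.** **Step 1: when the two rules disagree.** Count days from onset. Let s be the day on which maximal supportive care starts and r the day on which the event falls to Grade 2. The immune-mediated rule gives a DLT if r > 7. The gastrointestinal rule gives a DLT if r > s + 3. The deadlines coincide when s + 3 = 7, that is s = 4.

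| s | r | 7-day rule (r > 7) | 3-day rule (r > s + 3) |
|---|---|---|---|
| 0 | 5 | not met | met (5 > 3) |
| 3 | 5 | not met | not met (5 < 6) |
| 6 | 8 | met (8 > 7) | not met (8 < 9) |

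So for s < 4 the rules disagree when s + 3 < r ≤ 7, and for s > 4 when 7 < r ≤ s + 3. Early care makes the 3-day rule stricter; late care makes the 7-day rule stricter.

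**Step 2: reproduce Table 15.** Inputs from Section 6.6.1.2: prior Beta(1,1); posterior Beta(1 + a, 1 + n − a) for a DLTs in n participants; target 30%; equivalence interval (25%, 33%); a dose is unacceptably toxic (DU) if the probability that the DLT rate exceeds 30% is at least 80%. The scale is cut into intervals of length 0.33 − 0.25 = 0.08, with shorter remainders at the ends, and the decision follows the interval with the largest unit probability mass. Of the 54 possible cells for 0 to 4 DLTs, 48 match directly. The other six (0/1, 0/2, 1/1, 1/2, 1/3, 3/12) are the cells overridden by footnotes a, b, c and e. The table is therefore taken as printed.

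**Step 3: move one event from non-DLT to DLT in the printed table** (E escalate, S stay, D de-escalate).

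| n | first DLT (0 to 1) | second DLT (1 to 2) | third DLT (2 to 3) |
|---|---|---|---|
| 3 | E to S | S to DU | DU to DU |
| 6 | E to E | E to D | D to DU |
| 9 | E to E | E to E | E to D |

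At n = 3 the posterior probability that the DLT rate exceeds 30% is 0.24, 0.65 and 0.92 for 0, 1 and 2 DLTs. Over n = 3 to 12 and 0 to 4 DLTs, one extra DLT changes the decision in 2 + 2 + 2 + 2 + 2 + 3 + 2 + 2 + 2 + 1 = 20 of 39 comparisons. A first DLT changes the entry at n = 3 and 4 and at no n from 5 to 12.

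**Step 4: the other two uses.** Under Section 6.6.1, one immune-mediated event of Grade 2 or higher that has not fallen to Grade 1 within 72 hours already limits the next increment to 100%. If the same event is a DLT, the limit is 50%. This can matter even where the Table 15 letter stays at E. For the MTD, the observed rate at a dose with six participants is 1/6 = 16.7% or 2/6 = 33.3%, which is 13.3 or 3.3 percentage points from the 30% target before isotonic smoothing. A dose declared DU, such as 2/3, is excluded from MTD selection altogether (Section 6.6.4).

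**The case against.** The best reply is that both entries stand under one list of sufficient conditions, so meeting either makes the event a DLT, and failing to meet the 7-day entry exempts nothing. Exemptions have their own list, and diarrhea is not on it. The 7-day entry would still have work to do when care starts more than 4 days after onset. This reading is plausible, but it is not stated. It leaves the express 7-day allowance for immune-mediated diarrhea with almost no effect when care starts promptly, and it fits poorly with a default under which time limits operate as exceptions. A split between immune and non-immune diarrhea may have been intended, but that is not written either.

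Several stronger conclusions are tempting and should not be drawn.

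- A reader might infer that any event lasting 4 to 7 days is classified in opposite ways. The second row of the Step 1 table shows otherwise: with care from day 3 and Grade 2 by day 5, neither rule is met.
- A reader might rest the overlap on Appendix I: "In the absence of a clear alternative etiology, all such events should be managed as if they were immune-mediated". That sentence is a recommendation on management, not on DLT classification. The overlap follows from the definition in Section 6.6.3 and the list in Section 8.3.6.
- A reader might treat DLT incidence as the sole Part A primary endpoint or the only input to escalation. It is one of several primary endpoints. The Safety Review Committee reviews all relevant data before deciding (Section 6.6.7), and Section 6.6.1 has increment limits that do not depend on DLTs.

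The exposed set is also limited. Grade 3 non-infectious colitis is a DLT whatever its duration, so confirmed colitis is outside the overlap. In the single-participant cohorts the switch to mTPI-2 happens anyway, because any TEAE of Grade 2 or higher triggers it.

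**Conclusion.** The point holds in this form. Section 6.6.3 applies two rules to immune-mediated Grade 3 diarrhea, with different windows and clocks and no stated precedence, and the SAP does not resolve it. An event that falls to Grade 2 between the two deadlines meets one rule and not the other. The effect is greatest in small mTPI-2 cohorts: at 3 or 4 evaluable participants a first or a second DLT changes the Table 15 entry. It would be wrong to infer that the decision always changes, since 19 of the 39 comparisons do not.

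The conclusion assumes that Table 15 is applied as printed and that the event is judged immune-mediated under Section 6.6.3. The documents give no expected frequency for such events, so the number of affected decisions cannot be estimated.

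**What to change.** Reconcile the two entries in Section 6.6.3 on scope, window, clock start and precedence, so that each Grade 3 diarrhea event has exactly one DLT classification. Which rule applies is a clinical decision for the sponsor and the Safety Review Committee; this review does not propose one. In the SAP, point Section 4.5.10.1 to protocol Section 6.6.3 for the DLT definition.

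The edit is short, but the cost is more than editorial. Changes to the DLT definition in protocol Versions 2 and 3 were classed as substantial (Appendix L), so this one probably would be too. If escalation is already complete, a single documented classification is still needed for the DLT tables and the MTD estimate.
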